9. RESEARCH METHODS

[figure not shown]
9.1 STUDY DESIGN

This study is a multi-center, multi-country, non-interventional, registry-based post-authorization safety study (PASS) using secondary data collected as part of the Crovalimab Silo registry (Study MO44987) of participants with PNH exposed to crovalimab, including pregnant women and their infants.

Product-specific silos initiated by the IPIG can be created on request by the respective Marketing Authorization Holders (MAHs) and will include participants treated with PNH-specific therapy from a single MAH. These silos will be established to collect specific data on treated participants with PNH and address research objectives, which are treatment-related, and/or requests from regulatory authorities. The Crovalimab Silo

is a product-specific registry enrolling participants with PNH treated with crovalimab (see [Figure 1](#)).

Figure 1 Schematic Representation of the Primary Data Collection in the Crovalimab Silo Registry, a Product-Specific Registry of the Core Registry

IPIG = International Paroxysmal Nocturnal Hemoglobinuria Interest Group.

[figure not shown]
Participants enrolled in the Core Registry are expected to sign an Informed Consent Form for the purposes of that study. Following crovalimab treatment initiation, a separate privacy notice will be provided to the participants, which will explain in more detail how their data will be used, the specific data processing purposes, as well as the applicable legal bases for processing the data. Participants should acknowledge and receive the privacy notice to be part of the Crovalimab Silo.

The Crovalimab Silo will encompass retrospective and prospective data from all enrolled participants treated with crovalimab, including data from female pregnant patients and their infants. Patient demographics and medical history data will be collected at enrollment. Both prospective and retrospective data will cover participants' characteristics and clinical outcomes (including safety data, pregnancy and infant outcomes, and breastfeeding), and crovalimab exposure. For a visual representation of the data collection definitions for all participants with PNH, refer to [Figure 2](#).

Prospective data collection will commence at the initiation of treatment for participants who began therapy with crovalimab on or after the start of the Crovalimab Silo registry (illustrated as Patient A in [Figure 2](#)). For participants who began treatment with crovalimab before the Crovalimab Silo was established, retrospective data will be collected from the Core Registry into the silo, if available; while prospective data

collection will begin from the time of silo enrollment (illustrated as Patient B in Figure 2). The MAH anticipates very few cases in this last scenario.

Figure 2 Study Design for PNH in the Crovalimab Silo

IPIG = International PNH Interest Group; PNH = paroxysmal nocturnal hemoglobinuria.

The planned start date for the Crovalimab Silo refers to the date when information about the first participant in the Crovalimab Silo will be recorded in the database, which is projected to be in Q1 2026. The last data extraction and planned end of the registry, based on a planned data collection in the Crovalimab Silo, is projected in Q2 2032.

Participants' visit schedules will follow SOC. Participants' data are expected to be entered in the electronic data capture (EDC) system by the clinicians and/or their qualified designee at the time of registry enrollment and approximately every 6 months thereafter. In addition, participants and/or their parents/legally authorized representatives have the option to complete electronic patient-reported outcome (ePRO) questionnaires (i.e., the FACIT-Fatigue questionnaire) at registry enrollment, and every 6 months thereafter.

If a participant withdraws from the IPIG registry, the date and reason will be recorded in the electronic Case Report Form (eCRF), with efforts made to obtain this information. Registry site termination may happen due to inadequate participant recruitment or non-compliance with protocols, guidelines, or regulatory requirements. If a clinician withdraws, the MAH should be notified in advance, and a new clinician will be trained and identified to take over patient referrals.

9.2 SETTING

This study will analyze individual patient-level data gathered from multiple countries within the Crovalimab Silo. To date, the Crovalimab Silo plans to enroll participants from

Belgium, Canada, France, Germany, Italy, Netherlands, South Korea, Spain, United Kingdom, and the United States. China is under feasibility.

Index Date

The index date is defined as follows:

- To evaluate AESIs and other SAEs and AEs for all participants with PNH, the index date will be defined as the date of enrollment in the Crovalimab Silo.
- To characterize SAEs and AEs for women who are pregnant and pregnancy outcomes, the index date for these outcomes will be defined based on the pregnancy status at the time of silo enrollment. If the participant with PNH is pregnant, the index date will be the date of the silo registry enrollment. If the participant with PNH becomes pregnant after enrollment, the index date will be defined as the date of conception (DOC).
- To assess adverse fetal/neonatal/infant outcomes, SAEs, and AEs at birth and through at least the first year of the infant's life, the index date will be defined as the date of infant birth.
- For breastfeeding-related safety events, the index date will be defined as the date of initiation of breastfeeding for women who are in the Crovalimab Silo before breastfeeding starts or as the date of enrollment for women who join the Crovalimab Silo while breastfeeding.

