9.2.2 Inclusion/Exclusion Criteria

To evaluate AESIs and other SAEs and AEs for all participants with PNH:

Participants with PNH included in the SDU study will meet the same inclusion and exclusion criteria from the Crovalimab Silo listed below:

- Inclusion criteria:
 - Participants with PNH confirmed by flow cytometry.
 - Participant and/or parent/legally authorized representative provide written informed consent/assent to participate in the Core Registry and the Crovalimab Silo prior to any registry-related data collection, in a manner approved by the Institutional Review Board (IRB)/Independent Ethics Committee (IEC) and local regulations.
 - Participants with PNH currently being treated with or who start crovalimab during the study period.
- Exclusion criteria:
 - Participants with PNH participating in an interventional PNH clinical trial while receiving crovalimab (i.e., in combination with other therapy), with exception of

participants with PNH participating in the extension period of COMMODORE/COMPOSER Roche studies and Post Trial Access Programs.

The exclusion criteria for all participants will also be applicable to assess crovalimab exposure during pregnancy, as well as pregnancy, infant, and breastfeeding outcomes.

To evaluate AEs and SAEs during pregnancy and pregnancy outcomes:

The following additional inclusion criteria will be applicable:

- Crovalimab exposure during pregnancy or 9 months before DOC

To evaluate infant AEs and SAEs and infant and breastfeeding outcomes:

The following additional inclusion criteria will be applicable:

- Breastfeeding infant
- Infant younger than 12 months of age

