9.2.3 Participant Follow-up

The follow-up period will be the time period from index date (as defined in Section 9.2.1) until the end of the study or censoring, whichever comes first.

To evaluate AESIs and other AEs and SAEs for all participants with PNH, the date of censoring will be defined as the earliest occurrence of any of the following events:

- Consent withdrawal
- Site termination
- Crovalimab treatment discontinuation¹ (with an extra follow-up period after discontinuation)
- Enrollment into an interventional clinical trial²
- Death

To assess safety events during pregnancy and breastfeeding, including pregnancy and infant outcomes, additional censoring events will be defined:

- Date of delivery (for pregnancy safety and outcomes)
- First year of the infant's life (for safety and infant outcomes)
- On the date when breastfeeding stops or first year of the infant's life (for breastfeeding)

[figure not shown]
¹ For participants with PNH censored due to crovalimab treatment discontinuation, follow-up will continue up to 12 months if the participant does not start a new complement inhibitor or for 12 weeks if the participant starts a new complement inhibitor.

² To preserve the integrity of data collected for any interventional therapy for PNH in clinical studies, as well as to avoid duplicate safety reporting, participant data collection will be paused from the Crovalimab Silo and the Core Registry when participants enroll in an interventional clinical study for a PNH therapy.

Note: Safety events from the mother will continue to be recorded even after pregnancy ends, delivery, or the cessation of breastfeeding. Similarly, infant safety events will also continue to be recorded through their first year of age if breastfeeding is suspended.

Evaluation of pregnancy and infant outcomes during crovalimab exposure will rely on prospectively collected data within the Crovalimab Silo only for participants who enroll into the silo before being pregnant. However, for participants who enroll into the Crovalimab Silo while being pregnant, retrospective data on crovalimab exposure and outcomes will be incorporated into the silo, if such data are available from the Core Registry. Data for participants whose pregnancy outcomes occur before their enrollment in the Crovalimab Silo will not be obtainable. Very few instances are expected in these latter two scenarios due to the timing of drug approvals and site initiations in the Core Registry (see Figure 3).

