9.3.2.1.2 Spontaneous Abortion

A spontaneous abortion is defined as loss of a fetus due to natural causes at <20 weeks of gestation. Information on malformations will be requested if available.

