9.3.2.1.4 Fetal Death or Stillbirth (with or without Fetal Defects)

Fetal death or stillbirth refers to fetuses born dead ≥ 20 weeks gestation or weighing ≥ 350 grams ([\[ACOG\] American College of Obstetricians and Gynecologists Obstetric Care Consensus No 2020](#)). Fetal death occurring ≥ 20 weeks but ≤ 28 weeks gestation is considered an early fetal loss. Fetal death occurring > 28 weeks is considered a late fetal loss ([\[ACOG\] American College of Obstetricians and Gynecologists Obstetric Care Consensus No 2020](#)). If gestational age is unknown, stillbirth refers to a fetus weighing > 350 g.

Data from gross or pathological examinations of the abortus or fetus will not be available; however, presence of abnormalities will be recorded.

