9.7.1 Safety Analyses

No formal statistical testing will be performed. Descriptive statistics will be reported using summary tables and figures (where appropriate). Continuous variables will be summarized using mean, standard deviation, median, range (min–max) and interquartile range. Categorical variables will be summarized using counts and proportions (%).

Additionally, incidence and incidence rate (IRs; in person-years) and their 95% CIs of AESIs, SAEs and AEs will be calculated. The exact 95% CIs will be computed using the Clopper-Pearson method (Clopper and Pearson 1934). For the calculation of IRs, the denominator will be the pooled person-time of all the participants within the cohort. The patient time–at-risk will be calculated from index date until the date of an incident event or censoring, whichever occurs first. All first events occurring during follow-up period will be counted in the total number of events (thus, for each participant, only the first event will be counted) and divided by the total patient-years at risk. In addition, to IRs, incidence proportions will be calculated as proportion of participants with PNH afflicted with each of the AESIs, SAEs, and AEs up to the data extraction date.

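### For spontaneous abortion, the follow-up and frequency rules count women and person-time that can no longer have the event, so its frequency is understated

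*Protocol*

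**What the plan says.** **Start of follow-up.** Protocol 9.2 (Index Date) gives two starting points for pregnancy outcomes. A woman who conceives after entering the silo starts at conception. For a woman already pregnant, "If the participant with PNH is pregnant, the index date will be the date of the silo registry enrollment".

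**Who is included.** The only extra inclusion criterion for pregnancy outcomes in 9.2.2 is "Crovalimab exposure during pregnancy or 9 months before DOC". It places no limit on gestational age at entry.

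**End of follow-up.** Section 9.2.3 adds delivery as the censoring point for pregnancy safety and outcomes. It also states: "Data for participants whose pregnancy outcomes occur before their enrollment in the Crovalimab Silo will not be obtainable". It expects very few women to enroll while pregnant, or after the pregnancy outcome has occurred, and gives no number.

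**The outcome.** Section 9.3.2.1.2 defines spontaneous abortion as "loss of a fetus due to natural causes at <20 weeks of gestation". From 20 weeks a death is classed under 9.3.2.1.4: "Fetal death or stillbirth refers to fetuses born dead ≥ 20 weeks gestation or weighing ≥ 350 grams".

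**Frequency.** Under 9.7.1 a participant's time at risk runs from index date to event or censoring. For rates, "the denominator will be the pooled person-time of all the participants within the cohort". Incidence proportions are the share of participants affected. Section 9.7.2 adds trimester detail when feasible and a sensitivity analysis limited to prospectively collected events and exposure.

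**The concern.** A frequency is interpretable only if its denominator holds people, and time, at risk of the event. For spontaneous abortion these rules depart from that in three ways:

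- A woman who enrolls at, say, week 30 counts as a pregnant participant without a spontaneous abortion, although by definition she could not have had one while under observation.
- A woman who enrolls at week 12 is there only because the pregnancy reached week 12. Losses before enrollment are not captured, so entry is left-truncated.
- For every pregnancy, including those followed from conception, time from week 20 to delivery enters the person-time although the event is then impossible.

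All three push the estimate down. Spontaneous abortion is a primary variable, and Section 7 lists miscarriage among the pregnancy complications of PNH. Section 9.9.8 rules out comparison with other complement inhibitors in the registry, so the absolute frequency is itself the result and the error makes it look more favorable.

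**Working it through.** **The plan's own figures.** The only calculated figures in 9.5 are in Table 2, the chance of seeing at least one event among 300 participants. They reproduce from 1 − (1 − p)^300: 77.8% at p = 0.5%, 95.1% at 1.0%, 98.9% at 1.5% and 99.8% at 2.0%. The protocol gives no figure for fetal loss or for the precision of 25 pregnancies, so what follows rests on stated assumptions.

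**Inputs from the protocol.** About 25 pregnant participants (9.5); event possible only before 20 weeks (9.3.2.1.2); follow-up from index date to delivery (9.2, 9.2.3, 9.7.1).

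**Assumptions.** True risk r from conception of 10%, 15% or 20%; constant weekly hazard to week 20; delivery at 40 weeks; conception taken as week 0.

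**Step 1: proportion, entry at 20 weeks or later.** If a share f of the pregnancies enters at 20 weeks or later and the rest are followed from conception, the crude proportion is r × (1 − f).

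| Late entrants of 25 | f | r = 10% | r = 15% | r = 20% |
|---|---|---|---|---|
| 1 | 4% | 9.6% | 14.4% | 19.2% |
| 2 | 8% | 9.2% | 13.8% | 18.4% |

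The relative understatement equals f. For scale, 3 losses among 25 is 12.0% (95% Clopper-Pearson interval 2.5–31.2%). If 2 of the 25 entered at 20 weeks or later, the figure becomes 3/23 = 13.0% (2.8–33.6%).

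**Step 2: proportion, entry before 20 weeks.** With r = 15% the weekly hazard is λ = −ln(0.85)/20 = 0.00813. A woman entering at week 12 has a remaining risk of 1 − exp(−8λ) = 6.3%, not 15%.

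Now let 2 of 25 (8%) enroll while pregnant, with entry spread evenly over weeks 4–40 among pregnancies still continuing. Their average remaining risk is 2.93%, and 53.9% of them enter at 20 weeks or later.

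- Crude proportion: 0.92 × 15% + 0.08 × 2.93% = 14.0%.
- After excluding later entrants: 14.03% / (1 − 0.08 × 0.539) = 14.7%, still below 15%.

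Exclusion alone therefore does not remove the bias. Delayed entry is needed for the remainder.

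**Step 3: rate, women followed from conception.** With r = 15%, mean time per pregnancy is:

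- to event or week 20: 0.15 / 0.00813 = 18.5 weeks;
- to event or delivery: 18.5 + 20 × 0.85 = 35.5 weeks.

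The rates are 0.15/18.46 × 52 × 100 = 42.3 and 0.15/35.46 × 52 × 100 = 22.0 per 100 person-years, a ratio of 0.52. At r = 10% they are 27.4 and 14.1 (0.51), and at r = 20% they are 58.0 and 30.7 (0.53). This result does not depend on how many women enroll while pregnant.

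**The case against.** **The denominator is inferred.** The rules in 9.7.1 name AESIs, SAEs and AEs. Pregnancy outcomes are listed separately in the objectives, no denominator is written for spontaneous abortion, and 9.7.2 leaves full detail to a SAP that is not at hand. This stands as a limit on certainty. But 9.7.1 is the only frequency method offered for a primary objective, and 9.2 and 9.2.3 do fix the start and end of follow-up for pregnancy outcomes. A SAP that applied these rules unchanged would carry the fault forward.

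**The index date is not itself an error.** Correct. Starting at enrollment avoids counting unobserved event-free time and is the entry time a delayed-entry analysis needs. The trouble comes from combining it with the denominator and the censoring point.

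**Few women are concerned.** This stands for the proportion. A reader might suppose that several of the 25 pregnancies, or a large share of them, would be enrolled while pregnant. The protocol expects very few, and nothing in it supports a larger share.

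**Other analyses cover it.** They do not. Neither the prospective-only analysis nor the trimester detail removes late entrants from the denominator, and Core Registry data cannot restore pregnancies lost before enrollment.

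**Two wider readings fail.** A reader might extend the point to all fetal loss, but a woman entering at 20 weeks or later is still at risk of stillbirth. A reader might also say that trimester rates share the fault of late entry. Time at risk begins at the index date, so a woman enrolled in the second trimester adds no first-trimester time. Only trimester proportions, whose denominator is not stated, could be affected.

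**Conclusion.** The point holds for spontaneous abortion only. Applied as written, Sections 9.2, 9.2.3 and 9.7.1 count women and time not at risk, and the bias is downward.

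- **Proportion:** understated by the share entering at 20 weeks or later, and somewhat further by entry before 20 weeks. With one or two late entrants in 25 that is 4–8% in relative terms, small beside the sampling error of 25 pregnancies.
- **Rate:** roughly halved for every pregnancy, with a ratio of about 0.52 at an assumed 15% risk, constant hazard and 40-week delivery. This is the larger effect.

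The risk levels, the constant hazard and the number of late entrants are assumptions; the direction does not depend on them. It is worth correcting before the first analysis, but it does not threaten the study as a whole.

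**What to change.** In 9.7.1, state for spontaneous abortion that:

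1. time at risk runs from the later of conception and silo enrollment, and ends at 20 weeks of gestation at the latest;
2. pregnancies enrolled at 20 weeks or later are excluded from its denominator;
3. the cumulative proportion is estimated on the gestational-age scale with delayed entry at the week of enrollment;
4. pregnancies enrolled before conception are shown separately as a supporting estimate.

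For any trimester proportions, use women under observation in that trimester.

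The change is to analysis wording. Conception date, enrollment date and gestational age are already needed for the index dates and outcome definitions. The cost is a slightly smaller denominator and a wider interval: in the example above, 2.8–33.6% on 23 pregnancies against 2.5–31.2% on 25.

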9.2.1 Study Population

This SDU study will include all participants with PNH who are treated with crovalimab and have available data from the Crovalimab Silo, including participants who are pregnant and information from their infants.

9.2.2 Inclusion/Exclusion Criteria

To evaluate AESIs and other SAEs and AEs for all participants with PNH:

Participants with PNH included in the SDU study will meet the same inclusion and exclusion criteria from the Crovalimab Silo listed below:

- Inclusion criteria:
 - Participants with PNH confirmed by flow cytometry.
 - Participant and/or parent/legally authorized representative provide written informed consent/assent to participate in the Core Registry and the Crovalimab Silo prior to any registry-related data collection, in a manner approved by the Institutional Review Board (IRB)/Independent Ethics Committee (IEC) and local regulations.
 - Participants with PNH currently being treated with or who start crovalimab during the study period.
- Exclusion criteria:
 - Participants with PNH participating in an interventional PNH clinical trial while receiving crovalimab (i.e., in combination with other therapy), with exception of

participants with PNH participating in the extension period of COMMODORE/COMPOSER Roche studies and Post Trial Access Programs.

The exclusion criteria for all participants will also be applicable to assess crovalimab exposure during pregnancy, as well as pregnancy, infant, and breastfeeding outcomes.

To evaluate AEs and SAEs during pregnancy and pregnancy outcomes:

The following additional inclusion criteria will be applicable:

- Crovalimab exposure during pregnancy or 9 months before DOC

To evaluate infant AEs and SAEs and infant and breastfeeding outcomes:

The following additional inclusion criteria will be applicable:

- Breastfeeding infant
- Infant younger than 12 months of age

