Analyses will be presented separately for the entire PNH participant cohort, pregnant female participants with PNH, all infants, and infants categorized by breastfeeding status (yes/no). When feasible, these analyses will be further detailed according to each trimester of pregnancy and each quarter within the infant's first year of development. Additionally, where data allows, outcomes will be analyzed based on prior PNH treatment and using the classifications of naïve new users and prevalent new users.

Potential confounding factors influencing safety and pregnancy outcomes, such as demographic information (e.g., age, race/ethnicity), clinical characteristics, maternal medical history, obstetrical history, comorbidities, and concomitant medications will be used in subgroup analyses among participants with PNH who experience an AESI, as well as for pregnancy or infant outcomes. Adverse events of special interest proportions and incidence rates will be compared between subgroups. Similarly, subgroup analysis by clinical and laboratory test outcomes for PNH will be performed when feasible. Safety events will be also described by causality.

Sensitivity analysis will be performed restricting the data to safety events and crovalimab exposure that was collected prospectively only. The effects of the timing of crovalimab exposure before and during pregnancy and cumulative exposure periods on each outcome will be also evaluated as sensitivity analysis. Sensitivity analysis may also include timing variations of failure to thrive (FTT) and development deficiency outcomes, when available.

Full details on all statistical analyses, including other subgroup and sensitivity analyses, will be described in the Statistical Analysis Plan (SAP).

MILESTONES

FIRST DATA EXTRACTION:

The date of first data extraction is the date when the variables used for the data analysis as per protocol are extracted for the first time. The planned first data extraction is after 6 months of Crovalimab Silo inception. The planned first data extraction is in Q1 2026.

LAST DATA EXTRACTION:

The last data extraction is the date of the end of the Crovalimab Silo registry, plus an additional 6 months to account for final data transfer. The planned last data extraction is in Q2 2032.

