8.2 OBJECTIVES

The primary objectives for this study are as follows:

- To characterize and estimate the frequency of AESIs among participants with PNH exposed to crovalimab. AESIs are as follows:
 - Serious infections

- Meningococcal infection and other infections with encapsulated bacteria
- Development or worsening of any neurological condition (e.g., axonal neuropathy, multifocal mononeuropathy)
- Malignancies and hematologic abnormalities
- Serious hemolysis
- Transient immune complex reactions
- Infusion and injection-related reactions
- To characterize and estimate the frequency of AEs, SAEs, pregnancy outcomes, and infant outcomes in participants with PNH exposed to crovalimab during pregnancy and through breastfeeding. Specifically:
 - To estimate the frequency and further characterize all AEs, adverse pregnancy outcomes, and birth outcomes (during pregnancy until date of delivery), in pregnant female participants with PNH
 - To estimate the frequency and further characterize adverse fetal/neonatal/infant outcomes (e.g., major and minor congenital malformations, gestational age, postnatal growth and development) and SAEs at birth and through at least the first year of life of infants of mothers exposed to crovalimab during pregnancy
 - To estimate the frequency and further characterize all AEs for lactating females and infants exposed to crovalimab through breastfeeding

The secondary objectives for this study are as follows:

- To estimate the frequency and further characterize AEs and SAEs (not included as AESIs) in all participants with PNH exposed to crovalimab.
- To characterize clinical outcomes and laboratory test results relevant to PNH disease among participants with PNH who experienced an AESI
- To characterize patient-reported outcomes (PROs) among participants with PNH who experienced an AESI via a patient-reported fatigue assessment using the Functional Assessment of Chronic Illness Therapy (FACIT)-Fatigue questionnaire

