9.7.2 Subgroup and Sensitivity Analyses

Subgroup and sensitivity analyses will be implemented when sample size allows.

Analyses will be presented separately for all participants with PNH, for pregnant female participants with PNH, for all infants, and for infants sub-grouped by breastfeeding status (yes/no).

When feasible, analyses will be further detailed according to each trimester of pregnancy and each quarter within the infant's first year of development.

To account for previous complement inhibitor exposure, subgroup analyses will be also based on previous PNH treatment exposure, using the following definitions: "naïve new users" when individuals initiate crovalimab without prior exposure to C5 inhibitors, and "Prevalent new users" when individuals initiate crovalimab after having received at least one C5 inhibitor any time prior to crovalimab treatment start. Safety events will be also described by causality.

Potential confounding factors influencing safety and pregnancy outcomes, such as demographic information (e.g., age, race/ethnicity), clinical characteristics, maternal medical history, obstetrical history, comorbidities, and concomitant medications will be described among participants with PNH who experience an AESI, as well as for pregnancy or infant outcomes. If needed, subgroup analysis will be performed and AESIs proportions and incidence rates will be compared between subgroups.

Similarly, subgroup analysis may include clinical and laboratory test outcomes for PNH (e.g., MAVEs, HDA, BTH, etc.) and previous PNH treatment.

Sensitivity analysis will be performed restricting the data to safety events and crovalimab exposure that was collected prospectively only. The effects of the timing of crovalimab exposure before and during pregnancy and cumulative exposure periods on each outcome will be also evaluated as sensitivity analysis. Sensitivity analysis may also include timing variations of FTT and development deficiency outcomes, when available.

Full details on all statistical analyses, including other subgroup and sensitivity analyses, will be described in the Statistical Analysis Plan (SAP).

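### Section 9.2.2 makes breastfeeding a condition for all infant outcomes, contradicting the objective, index date, exposure window and planned all-infants analysis

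*Protocol*

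**What the plan says.** Section 9.2.2 has three criteria blocks: one for all participants, one for pregnancy, and one headed "To evaluate infant AEs and SAEs and infant and breastfeeding outcomes". The third block lists two additional inclusion criteria, "Breastfeeding infant" and "Infant younger than 12 months of age". Neither is tied to one class of outcome, and no alternative is offered between them. No other section gives an eligibility rule for infants.

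Other sections keep infant outcomes and breastfeeding outcomes apart:

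- Section 8.2 defines the infant objective by exposure in pregnancy, "through at least the first year of life of infants of mothers exposed to crovalimab during pregnancy". Breastfeeding is a separate objective: "To estimate the frequency and further characterize all AEs for lactating females and infants exposed to crovalimab through breastfeeding".
- Section 9.2 starts the infant clock at birth: "the index date will be defined as the date of infant birth". The start of breastfeeding, or enrolment while breastfeeding, is the index date only for breastfeeding-related events.
- Section 9.3.1.1 defines exposure for pregnancy and infant outcomes as running from 9 months before conception to delivery. It gives breastfeeding outcomes their own window.
- Section 9.7.2 plans separate analyses "for all infants, and for infants sub-grouped by breastfeeding status (yes/no"). The synopsis names the same sets: "all infants, and infants categorized by breastfeeding status (yes/no").

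**The concern.** The inclusion criteria are what a programmer uses to build a cohort. Programmed as written, the infant cohort contains breastfed infants only. The all-infants analysis then shrinks to breastfed infants, and the no group of the breastfeeding split has no never-breastfed infants in it.

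The harm goes beyond a smaller cohort. Breastfeeding comes after birth and can depend on how the infant is doing. Selecting on it means selecting on something close to the outcome. Neonatal death, serious infant infection, malformation, growth deficiency and developmental deficiency are all primary variables in section 9.3.2.1. An infant who dies before breastfeeding starts cannot enter the numerator at all. In a cohort this small, one missing event changes what the report says.

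**Working it through.** No figure in the protocol rests on this criterion, so there is none to reproduce. Table 2 concerns the 300 participants and does not bear on infants. The core of the check is a comparison of sections.

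**Step 1: are the two items cumulative?** The list for all participants in the same section (flow cytometry, consent, crovalimab treatment) plainly requires every item. Read the same way, an infant must be breastfed and under 12 months. If the items were alternatives, the breastfeeding item would add almost nothing, because breastfeeding follow-up and exposure end no later than the first birthday (9.2.3, 9.3.1.1), so a breastfed infant already meets the age item.

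**Step 2: does another passage admit never-breastfed infants?** The note in 9.2.3 keeps recording infant events to one year if breastfeeding is suspended. That presupposes breastfeeding had begun, and it concerns recording, not eligibility. Section 9.2.1 includes information from infants in general terms, but 9.2.2 then adds criteria for the infant analyses.

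**Step 3: direction of the bias.** Let s be the breastfed share, and r_b and r_n the risks in breastfed and never-breastfed infants.

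- All infants: s·r_b + (1 − s)·r_n
- Under 9.2.2: r_b
- Shortfall: (1 − s)·(r_n − r_b)

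Deaths before any breastfeeding fall wholly into r_n, so they are lost with certainty. For other first-year outcomes the shortfall is positive when r_n exceeds r_b. That is plausible, but it is an assumption; the protocol gives no data on it.

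**Step 4: illustration of size.**

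- From section 9.5: about 25 pregnant participants.
- Assumed: 25 live births, one per participant. Losses and terminations would lower this.
- Assumed: a breastfed share of 40% to 80%, so 25 × 0.40 = 10 to 25 × 0.80 = 20 eligible infants.

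The exact two-sided 95% upper limit with no events is 1 − 0.025^(1/n):

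- n = 25: 13.7%
- n = 20: 16.8%
- n = 10: 30.8%

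One death before any breastfeeding:

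- All infants: 1/25 = 4.0%, Clopper-Pearson 95% interval 0.1% to 20.4%.
- Under 9.2.2: 0/20 (upper limit 16.8%) or 0/10 (upper limit 30.8%). The event is absent from the estimate.

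**The case against.** The best defence is that the intent is plain. The block heading joins two outcome classes and is followed by two items, so the first could be meant for breastfeeding outcomes and the second for infant outcomes. Sections 8.2, 9.2, 9.2.3, 9.3.1.1 and 9.7.2 all keep the two classes apart, and Table 1 collects infant outcomes without any feeding condition. The study is descriptive, and no tested hypothesis is affected.

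Much of this stands. It shows that the restriction is a drafting conflict, and that the data would still be in the registry. It does not cure the conflict: the item-by-item pairing is not stated, and 9.2.2 is the only eligibility rule for infants.

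The same evidence rules out several stronger readings that a reader might infer:

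- *That the sponsor chose to study breastfed infants only.* The all-infants analysis is stated in both the synopsis and 9.7.2, which speaks against it.
- *That all early neonatal deaths, or all the worst outcomes, disappear.* A neonate breastfed before dying still qualifies. Stillbirths, terminations and live births with or without an anomaly can be reported under the pregnancy criterion, which has no feeding condition.
- *That the plan has no qualifying exposure for infants.* Section 9.3.1.1 defines it; 9.2.2 merely does not repeat it.

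**Conclusion.** The point holds as an internal contradiction. Section 9.2.2, followed literally, excludes never-breastfed infants of exposed mothers from a primary analysis, against 8.2, 9.2, 9.3.1.1 and 9.7.2. Deaths before any breastfeeding would be missed with certainty. The downward bias in other first-year outcomes rests on sicker infants being breastfed less often.

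The precision figures are illustrative only. The 25 in section 9.5 are pregnant participants, not infants, and the breastfed share is not in the protocol. With 20 live births, for example, the all-infants limit would itself be 16.8%, and half of them breastfed would give 30.8%. The contradiction does not depend on any of these numbers. It needs correcting because it decides who enters a primary-objective analysis.

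**What to change.** Split the third block of section 9.2.2 in two.

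1. **Infant outcomes:** every live-born infant of a mother who meets the existing pregnancy exposure criterion (crovalimab during pregnancy or in the 9 months before conception), from birth to 12 months, regardless of feeding.
2. **Breastfeeding outcomes:** infants under 12 months who are breastfed within the breastfeeding exposure window of 9.3.1.1. Define this set independently of the first. Making it a subset would drop infants exposed only through milk, such as those whose mothers started crovalimab after delivery.

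Keep breastfeeding yes/no in 9.7.2 as a descriptive stratum of the infant set.

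The cost is protocol wording only. Section 9.3.3 already collects breastfeeding status as yes/no, and the infant-outcome row of Table 1 already applies whatever the feeding, so no new data item is needed.
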